## 7.4 Data sources

Data will be collected using maternal interview(s), medical record review, pregnancy exposure diary, physical examination data, and neurodevelopmental questionnaire data (ASQ). Data will be recorded on hard copies of forms and these records will be retained by OTIS at the OTIS Research Center. These forms are considered the primary data sources for the study. Data from

these forms will be extracted and entered into a customized OTIS study database located in the Research Center and developed specifically for the OTIS studies. In addition, the Expanded Disability Status Scale (EDSS) (Koblet et al, 2006) assessing disease severity/activity will be administered to participants with MS, and collected from medical records when available.

Medications or vaccine exposures entered into the database will be coded using the Slone Drug Dictionary. Major malformations will be coding using the MACDP coding list. This coding system will be used in all annual interim and final reports, as well as the final analysis.

Safety data will be transferred to Novartis at a frequency as defined in [Section 9](#) of this protocol. An interim report will be provided annually to the Sponsor containing descriptive data only on characteristics of women enrolled in the study and cumulative study outcomes. No statistical comparisons are planned for the annual interim reports. The final report and statistical analysis report will be provided to the Sponsor after closure of the study.

#### **7.4.1 Data collected**

Data on the number of pregnant women referred into the study, number eligible for enrollment, number consented, unable to contact, or declined participation will be collected and summarized monthly by the OTIS Research Center.

#### **7.4.2 Disposition of patients**

Women who are not eligible for enrollment in the study or who decline are tallied in monthly and cumulative recruitment reports, but these data are not included in the annual interim or final study reports.

#### **7.4.3 Participant data**

The OTIS Research Center is responsible for verifying the subject selection criteria, enrolling each subject and securing informed consent (oral and written as applicable), providing all pregnancy and post-partum follow-up interviews and medical record review, scheduling dysmorphology physical examinations, obtaining questionnaire data, recording and storage of all data, and subsequent data analysis and interpretation.

##### **7.4.3.1 Intake/Enrollment interview**

Following oral informed consent, a structured maternal intake telephone interview will be conducted by a trained Research Associate at the OTIS Research Center. This interview will include questions on the following: pregnancy history; current health history; pre-pregnancy weight and height; socioeconomic and demographic information including maternal and paternal occupation, education and ethnicity, and income category; current medication use, both prescriptive and over the counter; other environmental or occupational exposures, alcohol, tobacco, caffeine and illicit drug use; current pregnancy complications including illnesses; and history of onset and other characteristics of the disease the participant is enrolled for, if applicable. Women who are enrolled with an indicated disease will be asked to respond to a severity assessment questionnaire that is specific to the approved indication to provide a means of assessing potential confounding or effect modification by disease severity in the final analysis.

### **7.4.3.2 Interim interview I and II (~20 and 32 weeks' gestation)**

Following the initial intake interview, participants will be sent a pregnancy exposure diary on which they will be asked to record any additional exposures (medications, vaccinations, vitamins, etc.) or events as the pregnancy progresses. Along with the pregnancy exposure diary, each woman will be sent a copy of the written informed consent document, and a research HIPAA compliant obstetric medical record release form.

Women who have enrolled in the study prior to 18 weeks post-LMP will be interviewed by telephone at 20-22 weeks post-LMP, 32-34 weeks post-LMP and within 0-6 weeks after the expected due date. Women who have enrolled between 18 and 20 weeks post-LMP will be interviewed at 32-34 weeks post-LMP and within 0-6 weeks after the expected due date.

Women who enrolled after 20 weeks post LMP and before 30 weeks post-LMP will be interviewed at 32-34 weeks post-LMP and within 0-6 weeks after the expected due date. Women who have enrolled after 30 weeks post-LMP will be interviewed within 0-6 weeks after the expected due date (See [Table 7-2](#)).

The purpose of these interviews will be to update records of pregnancy exposures and results of prenatal tests, to remind women to maintain the pregnancy exposure diary, to update phone number and address information, and to determine if the pregnancy has ended prior to the expected due date.

### **7.4.3.3 Pregnancy outcome interview**

At any of the interim interview points, if the pregnancy has ended, the outcome interview will be conducted at this time or at the earliest convenient time for the mother. For women who are still pregnant at the 32-34 week interview, the outcome interview will be conducted within 0-6 weeks after the expected due date.

The outcome interview for live born infants will be a structured telephone interview and information will be elicited on the following: date of delivery, hospital location and mode of delivery; sex, birth weight, length and head circumference; Apgar scores; description of delivery or birth complications including malformations; type and length of hospital stay for mother and infant; delivering physician's and infant physician's names and addresses; method of infant feeding; pregnancy weight gain; and additional exposures and results of prenatal tests occurring since the previous interview.

The outcome interview for spontaneous abortion or elective termination will also be structured and information will be elicited on the following: date and type of outcome; hospital location if applicable; prenatal diagnosis; pathology results if available; and additional exposures and results of prenatal tests occurring since the previous interview(s). The outcome interview for stillborn infants will include all of the above plus information on sex, birth size and autopsy results if available.

Major structural defects, spontaneous abortions, elective terminations, fetal or neonatal deaths occurring in the siponimod-exposed group will be reported to the sponsor within 24 hours of the Research Center staff learning of the event. These reports will be made using the FDA's MedWatch form. The sponsor will be responsible for directly reporting to the FDA and Health Canada for events involving their product according to regulatory guidelines (See [Section 9](#)).

#### **7.4.3.4 Medical records and general pediatric evaluation**

Upon completion of the outcome interview, each woman will be mailed a packet containing research HIPAA compliant medical records release forms for the delivery hospital, obstetrician, pediatrician, and specialty physician, if applicable. For women whose pregnancies have ended in spontaneous abortion, elective termination or stillbirth, records release forms will be mailed for prenatal diagnosis, pathology or autopsy reports if available. Each woman will be asked to sign the medical records release forms, as well as [REDACTED] HIPAA Authorization Addendum (if they or their child receives medical care at [REDACTED]), and to return these authorization documents along with the pregnancy exposure diary form.

Upon receipt of the signed medical records release forms, a standard physical evaluation form will be mailed to each pediatrician or other physician responsible for the care of each live born infant. This form includes information on infant size at the time of the latest examination and an open-ended question about postnatal complications including major structural defects and serious or opportunistic infections as defined in this protocol.

At one year of age, another research HIPAA compliant medical records release form for the pediatrician or healthcare provider caring for the child is sent to the mother for signature, and the signed form with a standard physical evaluation form is sent to the healthcare provider to request updated information on growth, major structural defects, and any serious or opportunistic infections as defined in this protocol up through one year of age.

#### **7.4.3.5 Dysmorphology evaluation**

All live born infants will be eligible for an exam by one of a team of study-dedicated dysmorphologists, led by the study Co-investigator, from the [REDACTED]. The team is made up of licensed pediatricians with subspecialty fellowship training in dysmorphology/genetics. The physical examinations evaluate infants for both major and minor structural defects and provide increased sensitivity for detecting a specific pattern of malformation should one exist. Infants will be examined within the first year of life or as soon as the examination can be practically arranged. The Research Center will group and schedule these follow-up examinations to meet the study criteria of infant age, to maximize physician blinding as to exposure status, and to minimize travel time and expense. The examiner travels to the patient to conduct the examination.

Infant examinations will be conducted using a standard checklist of approximately 130 minor malformations included in a standard physical evaluation form. In addition, with parental consent, digital photographs of the infant will be taken to aid in validating any findings across examiners.

Dysmorphologists will perform these examinations blinded to the exposure or comparison group status of the mothers. Because subjects may have visible evidence of their disease, the use of a disease-matched comparison group allows for preservation of physician blinding. Mothers are asked to sign a consent for medical photographs at the time of the examination. If deemed necessary, the examiners will meet to review photographs of children to assess any patterns that may be identified.

### 7.4.3.6 Achievement of developmental milestones

When the child is approximately one year of age, the mother will be asked to complete the ASQ developmental screening questionnaire (Squires et al, 2009).

### 7.4.3.7 Procedure and consequences for subject withdrawal

As stated in the informed consent, any study participant may withdraw from the study at any time for any reason; however, data that have been collected up to the time of withdrawal may be used. Women who withdraw from the study after the collection of birth outcome will not be considered lost-to-follow-up. Women who withdraw from the study prior to the collection of birth outcome will be considered lost-to-follow-up and the statistical analysis plan addresses the method whereby these data will be addressed.

### 7.4.4 Data collection schedule

Data will be collected according to the schedule described in Table 7-2 below. After oral informed consent, a maternal telephone interview is conducted. Depending on the gestational age at enrollment, up to two additional telephone interviews are scheduled in the second and third trimesters of pregnancy. Written informed consent is requested following the intake interview.

- An outcome telephone interview is planned for 0-6 weeks after delivery
- After the end of pregnancy, research HIPAA compliant medical records release forms for the obstetric provider, delivery hospital, pediatrician, and any specialty care provider for the indicated disease, are sent to the mother for signature. Once the record release forms are received, records are requested from the providers and upon their receipt, data are abstracted.
- A one-year pediatric evaluation release form will be sent to the mother and once signed will be used to request data from the pediatric care provider.
- Between birth and approximately one year of age (or as soon as the examination can be practically arranged), a dysmorphology examination will be scheduled.
- When the child of the participant is approximately one year of age, the participant will be asked to complete the ASQ for her child.

**Table 7-2 Timing of Cohort Enrollment, Interviews, Examinations, and Medical Records**

	Anytime In Pregnancy	20-22 Weeks' Gestation b	32-34 Weeks' Gestation c	0-6 Weeks Post-Delivery	0-12 Months Post-Delivery	1 Year Post-Delivery
Referral a	√					
Enrollment and Consent a	√					

Enrollment Interview a	√					
Interim Interview I		√				
Interim Interview II			√			
Pregnancy Outcome Interview and Request for Medical Records				√		
Medical Record Review					√	
Dysmorphology Examination					√	
Developmental Screening / ASQ						√
Pediatric 1-Year Medical Records Request and Review						√

aParticipants may enroll in the study anytime during pregnancy

bIf subject is enrolled and Intake Interview is conducted after 18 weeks' gestation, only one interim interview will be conducted during pregnancy at 32-34 weeks gestation

cIf subject is enrolled and Intake Interview is conducted at 30 weeks' gestation or after, no Interim Interview will be collected

## 7.5 Study size

Recruitment goals are set at an average of 34-36 subjects per year in each of the 3 groups as shown below in [Table 7-3](#), for a total of 867 subjects in the cohort, and an additional up to 50 subjects in the exposure series (anticipated recruitment not shown in the table), over a 7-year recruitment period. Balance in the cohort numbers will be monitored on a monthly basis, and overall balance addressed by adjusting recruitment activities as needed. It is not possible to predict the number of pregnancy exposures that will occur for a newly marketed medication, or that the recruitment rates will be equal in all years, and therefore, sample size is based on estimates that may require revision as the study progresses.

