## Study size

The prospective cohort study target sample size is 289 pregnant women who have been exposed to siponimod in pregnancy (i.e. on or any time after the 4th day post first day of the LMP prior to conception), for MS, 289 pregnant women diagnosed with MS not exposed to siponimod during pregnancy (primary comparison group/comparison group 1), and 289 healthy women i.e. women who are not diagnosed with MS, or any other autoimmune disease, and without exposure to siponimod, or any known human teratogen during pregnancy (secondary comparison group/comparison group 2).

The current sample size provides 80% power to detect a risk ratio of approximately 3.0 or greater in major structural defects with reference to the baseline prevalence of 2.8% in the Atlanta metropolitan area ([CDC 2017](#)).

Up to an additional 50 women will be enrolled in an exposure series group. This is a group of women with exposure to siponimod during pregnancy, but who do not meet eligibility criteria for the siponimod-exposed cohort group (e.g. retrospective cases would be in this group).

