The study population includes pregnant women who reside in the US or Canada with siponimod-exposure for the approved indication, and 2 comparison groups without siponimod exposure during pregnancy (1 disease-matched unexposed comparison group, and 1 healthy unexposed comparison group). Since the population under study (i.e. inclusion/exclusion criteria) are the same between this study (BAF312A2403) and the Kesimpta-OTIS pregnancy

registry sub-study (OMB157G2403) and the two studies will run in parallel using the same design, the comparator cohorts will be common between both studies. The first 125 pregnancies in the two comparison groups from the time of Kesimpta protocol (OMB157G2403) approval will be eligible for inclusion in both studies (i.e., the current study and the Kesimpta-OTIS pregnancy registry sub-study).

Based on use of multiple methods for identification and recruitment of exposed women, and the previous recruitment experience of the existing OTIS studies, the investigators have projected that approximately 17-18 pregnant women with exposure to siponimod could be enrolled in the Registry each year, although the true number of exposed pregnancies potentially available for enrollment in the Registry cannot be known at this time.

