**Table 7-3 Anticipated Recruitment Timetable and Sample Sizea,b**

Year 1	Year 2	Year 3	Year 4	Year 5	Year 6	Year 7
Enroll	Enroll	Enroll	Enroll	Enroll	Enroll	Enroll
34 Exposed	36 Exposed	36 Exposed	36 Exposed	36 Exposed	36 Exposed	36 Exposed
34 DMC	36 DMC	36 DMC	36 DMC	36 DMC	36 DMC	36 DMC
34 HC	34 HC	34 HC	36 HC	36 HC	36 HC	36 HC

aDisease-matched comparison (DMC)

bHealthy comparison (HC)

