### 7.5.1 Determination of sample size

The sample size for this study is not only based on the statistical considerations to address the question of interest but also takes into account the feasibility aspects, prior experience and available literature ([Krueger et al 2017](#)) on conduct of pregnancy registries in the MS disease area.

In the three cohorts, approximately 867 pregnant women will be enrolled in US and Canada with a ratio of 1:1:1.

Based on previous experience with MotherToBaby/OTIS Pregnancy Studies, it is estimated that subjects will be an average of 7-10 weeks post-LMP at the time of enrollment. Given this mean gestational timing at enrollment, the anticipated spontaneous abortion/stillbirth rate is 10%, the estimated elective abortion rate is 5%, and the estimated lost to follow-up rate is 5% ([Chambers et al, 2016](#)). This will result in known outcomes for approximately 273 pregnancies in each cohort, including 231 pregnancies with at least one live born infant in each cohort at the end of recruitment.

Baseline rates of major structural birth defects, specific patterns of three or more minor structural defects, premature delivery, and small for gestational age are based on previous MotherToBaby/ OTIS studies and on general population data. Rates of spontaneous abortion in the general population are 15-20% ([Avalos AL, et al 2012](#), and [Magnus et al 2019](#)). However, since women do not typically enroll in pregnancy registries until after 7-8 weeks' gestation when the highest risk of spontaneous abortion has passed, the baseline estimate is drawn from previous OTIS studies. [Table 7-4](#) gives the minimum detectable effect sizes with 80% power (two-sided significance level 0.05, except as noted below for pattern of minor structural defects), for the comparisons described above. If the disease-matched comparison and the healthy comparison groups are comparable, then consideration will be given to pooling data in the two comparisons cohorts for analysis, as shown in [Table 7-5](#). The current sample size provides 80% power to detect a risk ratio of approximately 4.4 or greater in major structural defects compared to the baseline prevalence of 3% in the comparison groups. This is consistent with the population prevalence of major structural defects of 2.8% in the Atlanta metropolitan area ([CDC 2017](#)).

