### 7.5.2 Interim feasibility assessment

An interim assessment to determine the feasibility of continuing the pregnancy registry will be conducted by the Sponsor at the end of three years from the start of the Registry and detailed in the separate SAP. At this interim assessment, data from the following sources will be examined in an integrated manner to determine the feasibility of continuing the pregnancy registry:

- Data from the Registry informing participant demographics (age distribution) and enrollment rate
- Data from secondary analysis of US real world data sources (such as Truven Health MarketScan) informing number and characteristics (age) of siponimod female patients, number of siponimod exposed pregnancies and live birth rate,
- Aggregate US marketing data informing the number and age distribution of US siponimod-exposed women
- Data from PRegnancy outcomes Intensive Monitoring program (PRIM – based on worldwide spontaneous reporting) informing number of pregnancies and outcomes from all over the world including US (for those reports that are not enrolled in the registry)
- Change in treatment landscape with availability of newly marketed drugs safer to use in pregnancy affecting the uptake of siponimod in women of child bearing potential

The integrated analysis of all these data will provide a basis for understanding the siponimod female patient population's characteristics and will help assess whether the scientific question of interest is at all relevant for the siponimod population and whether the Registry will be able

to answer the question in a reasonable timeframe (i.e. study results with targeted sample size with seven years of enrollment).

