#### **7.7.4 Year three interim feasibility assessment**

At the end of the third year from Registry initiation, feasibility will be re-assessed by the Sponsor. In particular, projections will be made to estimate the number of live births expected 10 years after launch (i.e. at target end date of study). This estimation will be done in an integrated manner taking into account all data sources as described in [Section 7.5.2](#).

As reference, if the projected number of live births after 10 years in the siponimod exposed cohort is less than 100, consideration will be made regarding study discontinuation. Note that these reference thresholds are indicative only and the final decision will be taken based on the totality of evidence accumulated until that point in time.

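### Table 7-3 sums to 746 women, not the 867 (289 per cohort) behind the power, and section 7.2 projects exposed enrolment at half the rate used in section 7.5

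*Protocol*

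**What the plan says.** The target appears in several places and is consistent among them. The abstract's Study size paragraph says "The prospective cohort study target sample size is 289 pregnant women who have been exposed to siponimod in pregnancy", with 289 in each comparison cohort. Section 7.5.1 says "approximately 867 pregnant women will be enrolled in US and Canada with a ratio of 1:1:1". From 289 enrolled, section 7.5.1 derives about 273 known outcomes and 231 pregnancies with a live birth per cohort. Table 7-4 uses 231 per group, a 3% comparator rate and a relative risk of 3.0 for 80% power, naming a two-sided Fisher's exact test at 0.05.

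The accrual side is in section 7.5: "Recruitment goals are set at an average of 34-36 subjects per year in each of the 3 groups", with a reference to Table 7-3, "for a total of 867 subjects in the cohort", over a 7-year recruitment period. The exposure series of up to 50 women is counted separately and is not in the table. Table 7-3, headed "Anticipated Recruitment Timetable and Sample Size", lists 34 or 36 women per group for each of seven years and prints no totals.

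Section 7.2 gives a different expectation for the exposed cohort, based on the planned recruitment methods and the network's previous studies: "approximately 17-18 pregnant women with exposure to siponimod could be enrolled in the Registry each year". It adds that the true number available cannot be known.

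**The concern.** The power statement depends on 289 enrolled per cohort. Section 7.5 presents the annual rate, the table, the 7 years and the 867 as one plan, so they should agree, and they do not. A registry that met its timetable in every year would still finish below its own sample size.

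The exposed cohort is the scarce one. For it the protocol holds two planning rates that differ by a factor of two, and neither yields 289 in the stated period. A reader cannot tell which enrolment the sponsor expects, and therefore which risk ratio the study could detect for major structural defects. The study answers a post-marketing requirement and has a feasibility assessment at year three. That assessment asks about results with the target sample within seven years of enrolment, so the figures it will be read against need to be consistent.

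**Working it through.** **Inputs.** Target 289 per cohort (abstract; 7.5.1). Rate 34-36 per group per year for 7 years (7.5). Yearly entries (Table 7-3). Exposed projection 17-18 per year (7.2). Losses of 10% spontaneous abortion or stillbirth, 5% elective abortion and 5% lost to follow-up (7.5.1). Comparator rate 3%, relative risk 3.0, two-sided 0.05 (Table 7-4).

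**The target reproduces itself.** 289 × 3 = 867. Live births: 289 × (1 − 0.10 − 0.05 − 0.05) = 231.2, stated as 231. Known outcomes: 289 × 0.95 = 274.6, stated as about 273.

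**The timetable does not reproduce the target.**

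| Cohort | Sum of Table 7-3 | Short of 289 |
|---|---|---|
| Exposed | 34 + 6 × 36 = 250 | 39 |
| Disease-matched | 34 + 6 × 36 = 250 | 39 |
| Healthy | 3 × 34 + 4 × 36 = 246 | 43 |
| Total | 746 | 121 (121/867 = 14.0%) |

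The rate range fails too: 34 × 3 × 7 = 714 and 36 × 3 × 7 = 756. The rate needed is 289/7 = 41.3 per group per year. At 36 a year, 289 takes 289/36 = 8.0 years.

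**The section 7.2 rate.** 17 × 7 = 119 and 18 × 7 = 126 enrolled. Multiplied by 0.80, these give 95 and 101 live births. Ten years of enrolment would give 170-180. Reaching 289 takes 289/18 = 16.1 to 289/17 = 17.0 years.

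**Power, with a same-method baseline.** Two methods are used because the printed 80% and the named test do not coincide.

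- Arcsine: power = Φ(h·√(n₁n₂/(n₁+n₂)) − 1.96), with h = 2·asin√0.09 − 2·asin√0.03 = 0.2612. At 231 per group: 0.2612 × 10.747 − 1.96 = 0.847, so 80.2%, which reproduces Table 7-4. At 200: 0.2612 × 10 − 1.96 = 0.652, so 74.3%.
- Fisher's exact test, by full enumeration: 74.0% at 231 and 66.4% at 200.

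| Live births, exposed v comparator | Power at 3.0, Fisher | Power at 3.0, arcsine | Detectable risk ratio, Fisher | Detectable risk ratio, arcsine |
|---|---|---|---|---|
| 231 v 231 (target) | 74.0% | 80.2% | 3.18 | 2.99 |
| 200 v 200 (250 × 0.80, Table 7-3) | 66.4% | 74.3% | 3.40 | 3.18 |
| 101 v 101 (18 a year) | 33.1% | 45.9% | 4.83 | 4.39 |
| 100 v 100 | 32.6% | 45.5% | 4.86 | 4.41 |
| 95 v 95 (17 a year) | 30.3% | 43.7% | 5.01 | 4.52 |
| 101 v 231 | 56.9% | 59.1% | 3.80 | 3.73 |
| 95 v 231 | 56.0% | 57.3% | 3.86 | 3.81 |

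The shortfall in Table 7-3 therefore costs 7.6 points by Fisher (74.0 − 66.4) or 5.9 by arcsine (80.2 − 74.3). The section 7.2 rate costs far more.

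**The case against.** The best defence is that the protocol admits its uncertainty. Sections 7.2, 7.5 and 7.9 all say that exposed pregnancies for a new drug cannot be predicted, and 7.5 and 7.9 say that the sample size may need revision. That excuses an uncertain forecast. It does not explain a table that fails to add to the total in its own introducing sentence, or two planning rates that differ twofold.

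It is also fair that the practical effect of Table 7-3 alone is modest. At 36 a year, 289 takes about 8 years. With roughly 1.75 years for pregnancy and infant follow-up (an assumption: 0.75 + 1.0), that is about 9.8 years, inside the planned 10.5. The stated 7 years would still be wrong.

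Setting 66.4% against the printed 80% would overstate the loss, because part of that gap is the difference between Fisher's test and the method that yields the printed figure. Only same-method differences are used here.

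Two stronger readings are tempting, and the protocol does not support them:

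- **That the year-three reference contradicts the target.** Section 7.7.4 says "if the projected number of live births after 10 years in the siponimod exposed cohort is less than 100", discontinuation will be considered, while section 7.5.2 speaks of "study results with targeted sample size with seven years of enrollment". But 7.7.4 equates ten years after launch with the study's target end date, which can mean 7 years of enrolment plus follow-up. On that reading 100 live births needs 100/0.80/7 = 17.9 women a year, and no slower accrual is implied. The reference is described as non-binding, with the decision left to all the evidence. A discontinuation reference below the target is not in itself an inconsistency.
- **That the plan contains remnants of a design of about 125 per cohort.** The 17-18 a year, the 100 live births and the risk ratio of 4.4 in section 7.5.1 do fit together: 4.4 has 80% power at 100-101 per group by arcsine, but 99% at 231. No section describes such a design. The only 125 in the protocol is the number of comparator pregnancies shared with the Kesimpta sub-study.

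**Conclusion.** The point holds in two parts. First, Table 7-3 and the 34-36 rate deliver 746 (range 714-756), not 867. This is plain addition and needs no assumption. Second, the exposed rate in section 7.2 is half that in section 7.5 and would yield 95-101 live births in 7 years against the 231 behind the power.

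The effect on power is moderate if the table is right: 74.0% to 66.4% (Fisher) or 80.2% to 74.3% (arcsine), with the detectable risk ratio moving from 3.2 to 3.4 or from 3.0 to 3.2. It is large if section 7.2 is right: 30-33% or 44-46% with equal groups, and a detectable risk ratio near 4.9 or 4.4 at 100 live births. If the comparison cohort still reaches 231, Fisher power is about 57%.

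These figures assume the protocol's 20% total loss, its 3% comparator rate and unadjusted comparisons. They do not extend to the year-three reference, which is not shown to be wrong.

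**What to change.** Choose one plan and make every figure follow from it.

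1. Either keep 289 per cohort, and correct Table 7-3, the annual rate and the recruitment period to match (about 41-42 per group per year for 7 years, or about 8 years at 36 a year). Or restate the target as 250/250/246 (746), with about 200 live births per group and the matching power and detectable risk ratio in section 7.5.1, Tables 7-4 and 7-5 and the abstract.
2. Print row totals in Table 7-3.
3. Reconcile the 17-18 exposed women a year in section 7.2 with the 34-36 in section 7.5, and say which is the planning rate.
4. State power and detectable risk ratio for the exposed number actually projected, naming the method used.

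This is an amendment to text and tables. It needs no new data collection. Keeping 289 within 7 years means a higher recruitment goal than the one now printed; the other routes mean a longer recruitment period or a weaker power statement. It is best done before the year-three feasibility assessment.
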